For critically ill patients admitted to an ICU, the mean overall nosocomial infection rate is 6 to 18% (29, 30, 40). The incidence rate of infection could be greater for all surgical ICU patients. The infection rate in the previous proof-of-concept study was 50% using the same population and inclusion/exclusion criteria; this assumption of equal proportions of prospectively enrolled infected and uninfected subjects will be used in the sample size calculations which follow. Data collected to date indicate that a sustained change in BDV of 1.0‰ or more correlates with the presence of infection when the subject is used as his-her control. The average intra subject standard deviation (SD) across time points in critically ill adult subjects previously studied was 0.95‰, regardless of the underlying medical conditions. The inter subject SD is expected to be 1.0‰ at most. Using the BDV measurements during the breath sample monitoring period (breath sample assessments every 4 hours), the expected overall SD of the mean BDV measurements (across time points) is less than 1.0‰.

BDV sensitivity and specificity will be evaluated relative to PCT sensitivity and specificity according to non-inferiority hypothesis tests where a greater than 10% BDV disadvantage is to be ruled for both sensitivity and specificity relative to a less than 10% BDV disadvantage. The BDV sensitivity and specificity estimates will then be used to determine the positive predictive value (PPV) and negative predictive value (NPV) once the prevalence is known; prevalence surrogates can be used to apply the observed sensitivity and specificity to various ICU and CCU settings.

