## **6. Analysis Sets/Populations/Subgroups**

The first task is to demonstrate that there is a positive signal associated with the Canary test using the subject as their own control.

A per protocol analysis will be performed following EAC event reconciliation and subsequent database lock. The EAC will determine diagnostic truth by documenting severe sepsis or septic shock events as well as the onset and resolution dates.

Infection documentation will be reviewed by the EAC committee based on best clinical practices, using four categories:

- No suspicion of infection
- Inconclusive evidence of infection
- High suspicion of infection
- Overt infection

For sensitivity and specificity, non-inferiority testing will be performed to rule out a -10% disadvantage according to a one-sided 97.5% lower confidence limit for the BDV – PCT

difference; exact McNemar paired comparison tests will be performed to test BDV non-inferiority relative to PCT. Both endpoints must achieve statistical significance in order to achieve study success.

PPV and NPV will be computed as observed and for a range of possible infection prevalence (10%, 20%, 30%, and 40%). Results will be analyzed in the same manner as sensitivity and specificity.

BDV variations will be assessed using a two-sample t-test to compare the averaged (across time points) BDV between subjects who are diagnosed with a severe sepsis and sepsis shock vs. no severe sepsis or sepsis shock. Also a linear mixed effects model with subject specific random effects will be used to compare BDV measurements between the two diagnostic groups. This model will be also used to estimate the intra- and inter-subject variability of the BDV measurements. A paired t-test will be used to compare the BDV measurements prior to and after a diagnosis of infection or sepsis.

The definition of a positive BDV will be based on a 72-hour window without advance knowledge of the diagnosis. In the absence of clinical details supporting PCT operating characteristics (sensitivity, specificity), two PCT thresholds (0.5 and 2.0) will be evaluated but the 0.5 threshold is deemed to be primary for BDV comparison.

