Descriptive statistics will be generated for patient characteristics, demographics, and on-study events relating to subgroups (see Section 7.4). For continuous variables, descriptive statistics may include the number of subjects from whom data was used in the calculation, mean, standard deviation, median, minimum, and maximum; frequencies and percentages may be displayed for categorical data.

The predicate marker PCT sensitivity is estimated to be between 64-82% based on a recent review of the published literature (19); PCT sensitivity will be assumed to be 75% for sample size calculations. BDV sensitivity is expected to range between 80-90% based on the proof-of-concept study. The study is designed to have at least 80% power and one-sided 2.5% Type I error. A greater than 10% disadvantage for BDV vs PCT (null hypothesis) is to be tested against a less than 10% disadvantage for BDV vs PCT (alternative hypothesis). As shown in Table 1, this non-inferiority hypothesis can be tested with 97 documented infection events. The BDV advantage vs PCT resulting in a -10% one-sided 97.5% lower confidence bound (CB) is also displayed in Table 1; if the sensitivities are 76.5% for BDV vs 75% for PCT based on 97 pairs of infection events, then the one-sided 97.5% lower CB would be -10%, which would establish BDV non-inferiority relative to PCT.

Table 1: One-sided 97.5% Lower 97.5% Confidence Limit: Sensitivity Paired Differences (simulation)

	Power	N-I
Confidence level, 1-<math>\alpha</math> (one-sided)	0.975	0.975
Expected difference, <math>\pi_T - \pi_S, \Delta_1</math>	0.100	0.015
Proportion discordant, <math>\eta = \pi_{10} + \pi_{01}</math>	0.400	0.315
Proportion both yes, <math>\pi_{11}</math>	0.600	0.600
Lower limit for <math>\pi_T - \pi_S, LL</math>	-0.100	-0.100
Number of simulations	1000	1000
Random seed for simulations	123	123

Power (%)	89	51
n (number of pairs)	97	97

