The predicate marker PCT specificity is estimated to be between 56-78% based on a recent review of the published literature (19); PCT specificity will be assumed to be 65% for sample size calculations. BDV specificity is expected to range between 70-80% based on the proof-of-concept study. The study is designed to have at least 80% power and one-sided 2.5% Type I error. A greater than 10% disadvantage for BDV vs PCT (null hypothesis) is to be tested against a less than 10% disadvantage for BDV vs PCT (alternative hypothesis). As shown in Table 2, this non-inferiority hypothesis can also be tested with 97 documented non-infection events. The BDV advantage vs PCT resulting in a -10% one-sided 97.5% lower confidence bound (CB) is also displayed in Table 2; if the specificities are 66.5% for BDV vs 65% for PCT based on 97 pairs of non-infection events, then the one-sided 97.5% lower CB would be -10%, which would establish BDV non-inferiority relative to PCT. A 10% non-inferiority delta with respect to both sensitivity and specificity ensures that the performance of BDV is comparable to PCT, considering the difference in sampling methods and the potentially greater convenience of breath sampling for BDV.

Table 2: One-sided 97.5% Lower Confidence Limit: Specificity Paired Differences simulation)

	Power	N-I
Confidence level, 1-<math>\alpha</math> (one-sided)	0.975	0.975
Expected difference, <math>\pi_T - \pi_S, \Delta_1</math>	0.100	0.015
Proportion discordant, <math>\eta = \pi_{10} + \pi_{01}</math>	0.400	0.315
Proportion both yes, <math>\pi_{11}</math>	0.100	0.100
Lower limit for <math>\pi_T - \pi_S, LL</math>	-0.100	-0.100
Number of simulations	1000	1000
Random seed for simulations	123	123
Power (%)	87	52
n (number of pairs)	97	97

We will also categorize infections per respiratory and non-respiratory infections within our data analysis to determine if there is an impact on the breath delta value.

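### The SAP's power of 80% or more per co-primary rests on 97 infection and 97 non-infection pairs, but it states no total N, and the documents do not show enrolment that yields those pairs

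*SAP*

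**What the plan says.** SAP section 6 sizes two paired non-inferiority comparisons of BDV with PCT, with a margin of 10 percentage points.

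- Sensitivity: "this non-inferiority hypothesis can be tested with 97 documented infection events". Specificity: "this non-inferiority hypothesis can also be tested with 97 documented non-infection events".
- Power, stated in the same words for both: "The study is designed to have at least 80% power and one-sided 2.5% Type I error".
- Tables 1 and 2 take an expected advantage of 0.10 and a discordant proportion of 0.40, and report 89% and 87% power at 97 pairs.
- Expected performance: "BDV sensitivity is expected to range between 80-90% based on the proof-of-concept study", against PCT at 75%; and "BDV specificity is expected to range between 70-80% based on the proof-of-concept study", against PCT at 65%. The anticipated advantage is therefore 5 to 15 points on each endpoint.
- Success rule: "Both endpoints must achieve statistical significance in order to achieve study success".
- Reference standard: "The EAC will determine diagnostic truth by documenting severe sepsis or septic shock events as well as the onset and resolution dates".

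SAP section 5 adds that "this assumption of equal proportions of prospectively enrolled infected and uninfected subjects will be used in the sample size calculations", citing a 50% infection rate in the proof-of-concept study. The SAP gives no total number of subjects.

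Protocol 7.1 plans 100 subjects, with an enrolment target of 110 to allow for up to 10% loss. Protocol 3.0 says that up to 100 will be enrolled. The 100 is justified by a comparison of mean BDV between 5 infected and 95 non-infected subjects, with 10% infected as an alternative.

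**The concern.** A power claim can be checked only against the number of observations the study will have. Here the claim is in one document and the only enrolment figure is in the other, where it was derived for another test at another infection rate. Nothing connects 97 + 97 pairs to 100 subjects.

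Three further points are open: whether a subject contributes one pair or several; whether an infected subject's infection-free time also supplies a non-infection pair; and whether the event is infection (as in the sizing text) or severe sepsis or septic shock (as in the hypotheses and the adjudicated truth). Each changes the pair count.

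Both co-primaries must succeed, so the stated power bears on how a failed criterion would be read. If fewer pairs are available than the tables assume, a miss could reflect the pair count rather than the device.

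**Working it through.** **Inputs.** From SAP section 6: margin m = 0.10, one-sided 2.5%, difference d = 0.10, discordant proportion η = 0.40, n = 97 pairs. From SAP section 5: 50% infected. From Protocol 7.1: N = 100, and 5% or 10% infected. Correlations, and discordances other than 0.40, are assumptions and are marked as such.

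**Method.** The approximate formula is power = Φ((d + m)/√((η − d²)/n) − 1.96). The results below come from exact enumeration of the paired table with the score test for a difference of −0.10.

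**1. Reproduce the SAP.** At n = 97 the standard error is √(0.39/97) = 0.0634. Then 0.20/0.0634 − 1.96 = 1.19, and power is 88.4%. The exact score test gives 88.1%. The SAP reports 89% and 87% from 1,000 simulations, so the tables hold at 97 pairs.

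**2. Subjects implied.** At one pair per subject and equal proportions, 97 + 97 = 194 evaluable subjects. At d = 0.10 and η = 0.40, 80% per endpoint needs 79 pairs each (exact power 80.7%; 78 pairs give 79.9%), or 158 subjects. In the protocol, 110 less 10% is 99, in effect 100.

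**3. Power at N = 100, one pair per subject, d = 0.10, η = 0.40.**

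| Infection rate | Sensitivity pairs | Power | Specificity pairs | Power |
|---|---|---|---|---|
| 50% (SAP 5) | 50 | 61.5% | 50 | 61.5% |
| 10% (Protocol 7.1) | 10 | 15% | 90 | 85% |
| 5% (Protocol 7.1) | 5 | 7% | 95 | 87% |

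At 50 + 50 the two endpoints use different subjects, so joint power is 0.615² = 0.378, about 38%.

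**4. Effect of difference and discordance at 50 pairs.** Table 1's both-positive proportion is 0.60, so a discordance of 0.40 is the largest possible and the least favourable for sensitivity. If the two tests were independent given infection (assumed), η = 0.85 × 0.25 + 0.15 × 0.75 = 0.325, and sensitivity power is 70%. The other discordances below are assumed.

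| Difference | Discordance | Power at 50 pairs |
|---|---|---|
| +5 | 0.40 to 0.35 | 39% to 43% |
| +13 | 0.34 | about 80% |
| +15 | 0.40 (specificity) | 81% |
| +15 | 0.35 (sensitivity) | 86% |

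For comparison, 97 pairs give 65% to 70% at +5 points (discordance 0.40 to 0.35).

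**5. Infection-free periods also counted.** Specificity could then have up to 100 pairs, about 89% power at d = 0.10 and η = 0.40. Sensitivity stays at 50 pairs and 61.5%. Treating the endpoints as independent (a simplification, since subjects now overlap), joint power is 0.615 × 0.89 = 0.55.

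**6. Repeated events counted.** Reaching 97 infection pairs from 50 subjects needs 97/50 = 1.94 per subject. With design effect 1 + 0.94 × ICC:

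| ICC (assumed) | Effective pairs | Power |
|---|---|---|
| 0.1 | 88.7 | 85% |
| 0.2 | 81.6 | 82% |
| 0.3 | 75.7 | 78% |
| 0.5 | 66.0 | 73% |

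**7. Severe sepsis or septic shock as the event.** If 80% or 60% of 50 infections progress (assumed), sensitivity has 40 or 30 pairs, and power of about 49% or 41%.

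**The case against.** On its own terms the SAP is coherent: 97 + 97 at equal proportions implies 194 subjects and about 88% power per endpoint. It never says that 100 subjects will supply those pairs. It counts events, which is ordinary event-based sizing, and its interim section allows enrolment to be targeted at particular subgroups. The eligibility criteria, the definition of a positive BDV and the assumed SD also differ between the documents, so the SAP may have been written for another protocol version.

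Much of this stands. A reader might infer that the trial has 61% power for each endpoint. The documents do not support that as a finding: 50 + 50 joins the protocol's N to the SAP's infection rate, and neither document states that split. A reader might also infer that 80% is out of reach with 100 subjects. That does not follow either. Under repeated events with modest clustering power stays at 82% to 85%, and at one pair per subject sensitivity reaches about 80% near +13 points.

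The objection does not remove the gap. A version mismatch would explain the missing link without supplying it, and event-based sizing still needs an enrolment or a stopping rule that delivers the events. Section 5's wording about infected and uninfected subjects leans towards one pair per subject. If events repeat, neither the tables nor the McNemar test as written allows for within-subject correlation.

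**Conclusion.** The power statement is unsupported as the documents stand. This is an inconsistency between the protocol and the SAP together with an unstated N; it is not an arithmetic error in Tables 1 and 2.

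The firm part is this: 97 + 97 pairs at one per subject and an equal split need 194 evaluable subjects, and the only planned number is 100, set for another test. The power figures for N = 100 are conditional illustrations. For sensitivity at the SAP's design point they run from about 7% (5% infected, one pair each) through 61% (50% infected) to 85% (repeated events, ICC 0.1). Specificity runs from 61% to about 89%. Confidence is high that the gap exists and moderate for any single power figure, because each rests on a counting unit, event rate and discordance that the documents do not settle.

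The SAP makes no claim about joint power. Because both endpoints must succeed, it is nevertheless the figure that describes the chance of study success. Even at 97 + 97 it is about 0.89 × 0.87 = 77% if the endpoints are independent.

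**What to change.** Reconcile Protocol 3.0 and 7.1 with SAP sections 5 and 6 on:

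- one total N, including whether 100 or 110 are to be enrolled;
- one assumed event rate for the population actually enrolled;
- one reference event, either infection or severe sepsis/septic shock;
- one counting unit, saying whether infection-free periods of infected subjects count, with a clustering adjustment if events repeat.

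State that N in the SAP. Replace the general 80% claim with the per-endpoint power that N delivers across the SAP's 5 to 15 point range, give the discordance used, and add the joint power. Keep the 80% statement only if the reconciled N and unit support it. Which N governs is the sponsor's choice.

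The cost is wording in two documents and a short recalculation. No extra subjects are required unless the sponsor decides to raise N. The downside is that the stated power may be lower.

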## 7. Endpoints and Covariates

We divided the covariates into two categories: the first is related to baseline covariates, such as underlying medical conditions, caloric intake, infection history, immune markers, being on antibiotics, and other concurrent therapies at baseline. Baseline medical conditions will be collected per the Charleston Comorbidity Index. The second category is related to on-study covariates (possibly outcome correlative) like procalcitonin, new antibiotics, new surgeries, new treatments, changes in diet, healing rates, and clinical signs and symptoms (e.g. fever, chills, WBC, breaths per minute, pulse, electrolytes).

While we recognize that some of the aforementioned covariates can affect sample carbon dioxide concentration (ventilator settings, or exogenous oxygen), any diluents will affect both  $^{13}\text{CO}_2$  and  $^{12}\text{CO}_2$  proportionally and will not disturb the  $^{13}\text{CO}_2$ : $^{12}\text{CO}_2$  ratio. Similarly, covariates that compromise air exchange in the lung do not affect the ratio of  $^{13}\text{CO}_2$ : $^{12}\text{CO}_2$  since there is no fractionating process during the exchange process. As long as the patient is producing  $\text{CO}_2$ , there will be exhaled  $\text{CO}_2$  albeit at potentially lower concentrations in subjects with reduced air exchange capacity, but the relative ratio of  $^{13}\text{CO}_2$  to  $^{12}\text{CO}_2$  remains constant. These points being stated, we have modified our study design to collect the necessary covariate data to demonstrate that  $\text{CO}_2$  concentration does not affect the  $^{13}\text{CO}_2$ : $^{12}\text{CO}_2$  ratio, by capturing the following information and the changes to these:

- **Ventilator settings** (Ventilator Mode, Oxygen Concentration, PEEP setting, Tidal Volume/Pressure,  $\text{FiO}_2$   $\text{PaO}_2$  and Flow Rate)
- **Lung dysfunctions** (Baseline comorbidities and diagnosed lung dysfunctions)
- **Nutrition and metabolic status** (Type of Nutrition, Type of Line, and Composition)
- **Comorbidity** (COPD, diabetes, metabolic and lung dysfunction)

## 8. Handling of Missing Values and Other Data Conventions

The number of missing samples will be minimized, but some samples will be missed due to clinical care logistics. A complete case analysis will be the primary analysis. An imputation based analysis will be a secondary analysis. Specifically, the last observation carried forward (LOCF) and multiple imputation method based on the Markov Chain Monte Carlo technique will be utilized to perform the imputation based analyses. A sensitivity analysis will be conducted to compare the results of the complete case analysis with the results of the imputation based analysis.

### Interim analysis plan

After completion of 25 subjects, an interim analysis will be done to ensure subject safety and to assess positive predictive value of the BDV for progression to severe sepsis and septic shock. If no subject progressing to sepsis or septic shock subjects had a positive BDV test, then additional enrollment will be stopped, and inclusion criteria will be reviewed. The study will not be stopped for superiority.

Subject safety will be assessed. If any significant risks to subject safety are identified, then additional enrollment will be stopped, and safety considerations will be assessed. During interim data analysis subgroups will be reviewed. Particular subgroups will be targeted for enrollment as necessary.

## 9. Statistical Methodology

Descriptive statistics will be generated. For continuous variables, descriptive statistics may include the number of subjects from whom data was used in the calculation, mean, standard deviation, median, minimum, and maximum; frequencies and percentages may be displayed for categorical data.

A 2-sample t-test will be used to compare the averaged (across time points) BDV between subjects who are diagnosed with an infection, without an infection, with sepsis and without sepsis. A linear mixed effects model with subject specific random effects will be used to compare BDV measurements between infected and non-infected and septic and non-septic subjects. This model will be also used to estimate the intra- and inter-subject variability of the BDV measurements. A paired t-test will be used to compare the BDV measurements prior to and after a diagnosis of infection or sepsis. Fisher's exact test and the Kappa statistic will be used to evaluate the relationship between a positive indication of infection by the BDV and a diagnosis of infection or sepsis in the subsequent 72 hours. Sensitivity, specificity, negative predictive value, positive predictive value and corresponding 95% confidence interval will be calculated.

## 10. Rationale for any Deviation from Pre-specified Analysis Plan

Not applicable at this time.

## 11. QC Plans

- Study personnel will complete sample collection and sample analysis records to ensure proper sample collection analysis and data reporting for each subject enrolled.
- When a new subject is enrolled in the study, the study team member will label and complete the sample collection records with the subject's study number.
- The study team member will notify Isomark personnel by email that a new subject is enrolled.
- At each subsequent breath collection time, a study team member will label the breath sampling equipment with the subject study number, site number, date and time when each sample was collected. The study team member will complete and initial the relative collection records within the Case Report Form (CRF). If the sample is obtained late, then the reason will be documented, e.g. subject in MRI. Each breath sample will be collected as close as possible and not exceeding one hour prior to or after the designated time for the sample collection.
- At each blood collection time, a study team member will label blood sampling equipment with collection date and time. Isomark will provide pre-printed labels with each subject's study number. The study team member will complete and initial the blood sample collection record, accounting for the time of collection, time of spinning, and time of freezing. The total time between collection and freezing cannot exceed four hours. If a sample is not collected on a given day, it will be considered missing data.

- A study team member will collect a breath sample every four hours and a blood sample daily for the study duration specified.
- Collected breath samples and the original copies of the corresponding sample collection records will be stored until analyzed on-site. Remaining sample will be shipped to Isomark.
- Blood samples and the original copies of the corresponding blood sample collection records will be placed in an Isomark-provided container and shipped to Isomark's contracted reference lab via an Isomark-approved carrier. The blood samples are processed by the reference lab and the results are sent to the sites, and will need to be entered into the EDC by the site staff. After the results have been successfully received, the lab will dispose of any remaining blood samples.
- Each time breath samples are received, labels will be checked for complete information and compare the samples to the EDC, noting anomalies. Any discrepancies will be cleared up between the site staff, contracted laboratory and Isomark personnel.
- At the beginning of each day on which samples are analyzed, the sample analysis technician will ensure the Canary is within calibration specifications by analyzing a standard sample of known isotopic composition and initial the sample analysis record.
- Breath samples are to be analyzed within 21 days of the time of collection. Isomark personnel will note the time and date of sample analysis on the sample analysis record and initial.
- Data will be recorded on the machine, and a verification code will populate the screen. The verification code will be recorded by the technician.
- Data that is extracted from the machine on regular intervals by Isomark designated personnel, will be recorded on an applicable log and cross checked to the technician's log. Discrepancies will be addressed and mitigated as soon as possible.

